5.1 Study Arm 1 Z-Endoxifen HCl

	Prior to pre-registration	Pre-registration Period (any time during days -28 to -1)	Days 1 of each treatment cycle*	At PD or discontinuation of protocol therapy**
Tests & Observations				
History and physical, weight, PS	X		X	X
Height	X			
Pulse, Blood Pressure	X		X	X
Adverse Event Assessment			X	X
Patient Medication Log			X(1)	X(1)
Registration Fatigue/Uniscale Assessment		A		
Standard of care biopsy of either locally recurrent or metastatic breast cancer is required for determination of ER, PR and HER2		B		
Laboratory Studies				
AST, creatinine, Total Bilirubin	X	X	X	X
Complete Blood Count, Differential, Platelets	X	X	X	X
Albumin, Alk Phos, ALT, calcium, glucose, phosphorous, sodium, potassium,		X	X	X
Fasting lipid profile (total Cholesterol, LDL, HDL, triglycerides)		C	C	
Imaging Tumor Measurements/Evaluation of Indicator Lesions				
CT/MRI		D, E, F	D,	D, E
Bone Scan/PET-CT scan		D, E, F	E	E
Correlative Studies: For Patients who consent to participate				
Tissue and Blood samples	See Sections 6.0 and 14.0 .			

* Cycle length is 21 days. Labs completed prior to registration may be used for day 1 of cycle one tests if obtained ≤ 21 days prior to treatment. For subsequent cycles, labs, scans, tests and observations may be obtained no more than +/- 3 days prior to day 1 of treatment.

** After treatment discontinuation, patients will be followed yearly for a maximum of 5 years from study registration/randomization (see Section [12.3](#)).

1. Medication Log must begin on the day the patient begins study medication and must be completed per protocol until treatment discontinuation (see Section [7.4](#)).

- A. To be completed after Pre-registration and prior to treatment, and will take approximately a minute to complete (see Section [1.8](#) and [Appendix I](#)).
- B. A standard of care biopsy of locally recurrent or metastatic breast cancer during the pre-registration period is required to confirm ER, PR and HER2 status by an institutional/local pathologist and for submission of a research block for optional correlative studies. **However**, if a prior biopsy was performed on a locally recurrent/metastatic site within 90 days of pre-registration, and no anti-cancer therapy was administered during that time period, that specimen can be used for confirmation of ER/PR/HER2 and for submission of tissue for optional correlative studies.

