- C. Lipid profile is required at Pre-registration (baseline), cycles 2, 4 and 8 and thereafter at the discretion of the treating physician.
- D. Acceptable imaging modalities for measurable disease include: a CT, spiral CT, MRI, and chest x-ray. A FDG-PET scanning is allowed to complement CT scanning in assessment of progressive disease.
- E. Tumor measurements are required during the pre-registration period (days -28 to -1), at completion of cycles 2, 4, and 6 (approximately, every 6 weeks) then every 4 cycles (approximately every 3 months) thereafter until disease progression, as determined in Section [11.0](#). The same imaging method utilized at baseline must be used at all disease assessments and must include all target and non-target lesions recorded at baseline.

For patients without bone metastases, bone scans after the baseline bone scan are at the discretion of the treating physician. See Section [11.0](#) for acceptable modalities for tumor imaging.

For patients with non-measurable bone only disease, follow-up imaging either with PET/CT or bone scan should be performed at the time of tumor assessment. The same imaging method utilized at baseline must be used at all tumor assessments.

- F. Need not be repeated if performed before pre-registration period, but not more than 28 days prior to registration.

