The specimens will be collected at the following time points:

- 1) Cycle 1, Day 1 prior to the start of treatment
- 2) End of Cycle 2, (prior to the start of Cycle 3)
- 3) End of Cycle 8, (prior to the start of Cycle 9)
- 4) At the time of disease progression

For those patients with crossover from tamoxifen to Z-Endoxifen HCl, CTC samples will be collected as follows:

- 1) End of Cycle 2, (prior to the start of Cycle 3)
- 2) End of Cycle 8, (prior to the start of Cycle 9)
- 3) At the time of disease progression

Two 10 mL blood samples will be collected in K2-EDTA tubes CTC specific kits will be used for this study. **Once a patient has been Pre-registered one ST-2 kit should be ordered for per patients, using the A011203 Biospecimen Accessioning Processing Fax Order Form, which may be downloaded from the A011203 study page of the Alliance and the CTSU web sites.** Instructions for processing these blood samples are provided in the blood specimen collection kits and **must be followed** in order for the samples to be viable.

Samples should be kept at ambient temperature after collection and during shipping. Ship CTC sample and cfDNA samples together to:

BAP Freezer
Mayo Clinic
[name]
[name]
[name]
[contact]

Samples for the CTC studies should be collected and shipped Monday – Thursday. However, if the subject can only be seen on Fridays, please contact the Biospecimen Resource Manager [name] for additional instructions [contact], Email: [contact].

Circulating Cell Free DNA Isolation and Analysis (cfDNA)

The specimens will be collected at the following time points:

- 1) Cycle 1, Day 1 prior to the start of treatment
- 2) End of Cycle 2, (prior to the start of Cycle 3)
- 3) End of Cycle 8, (prior to the start of Cycle 9)
- 4) At the time of disease progression

For those patients with crossover from tamoxifen to Z-endoxifen HCl, cfDNA samples will be collected as follows:

- 1) End of Cycle 2, (prior to the start of Cycle 3)
- 2) End of Cycle 8, (prior to the start of Cycle 9)
- 3) At the time of disease progression

Two 10 mL blood samples will be collected in Streck Cell Free DNA BCT tubes. These samples will be processed within 7 days of collection for cfDNA extraction and subsequent analyses. All of these samples must be labeled for immediate processing. The Streck Cell Free DNA BCT tubes will be provided for this study TBD...

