11.4.4 Overall Objective Status

The overall objective status for an evaluation is determined by combining the patient’s status on target lesions, target lymph nodes, non-target lesions, non-target lymph nodes, and new disease as defined in the following tables:

For Patients with Measurable Disease

Target Lesions & Target Lymph Nodes	Non-Target Lesions & Non-Target Lymph Nodes	New Sites of Disease	Overall Objective Status
CR	CR	No	CR
CR	Non-CR/Non-PD	No	PR
PR	CR Non-CR/Non-PD	No	PR
CR/PR	Not All Evaluated*	No	PR**
SD	CR Non-CR/Non-PD Not All Evaluated*	No	SD
Not all Evaluated	CR Non-CR/Non-PD Not All Evaluated*	No	Not Evaluated (NE)
PD	Unequivocal PD CR Non-CR/Non-PD Not All Evaluated*	Yes or No	PD
CR/PR/SD/PD/Not all Evaluated	Unequivocal PD	Yes or No	PD
CR/PR/SD/PD/Not all Evaluated	CR Non-CR/Non-PD Not All Evaluated*	Yes	PD

* See Section [11.4.3.1](#)

11.4.5 For those patients with non-measurable, bone-only disease, objective progression will be established if at least 1 of the following criteria is met:

- the appearance of 1 or more new lesions (in bone or outside of bone), or
- unequivocal progression of existing bone lesions.

The finding of a new lesion should be unequivocal and not attributable to findings thought to represent something other than tumor (for example, some ‘new ributab lesions may be simply healing or flare of preexisting lesions). Pathologic fracture, new compression fracture, or complications of bone metastases will not be considered as evidence of disease progression, unless at least 1 of the above criteria is met.

11.4.6 Symptomatic Deterioration: Patients with global deterioration of health status requiring discontinuation of treatment without objective evidence of disease progression at that time, and not either related to study treatment or other medical conditions, should be reported as PD due to “symptomatic deterioration.” Every effort should be made to document the objective progression even after discontinuation of treatment due to symptomatic deterioration.

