13.0 STATISTICAL CONSIDERATIONS**13.1 Study Design**

A randomized phase II clinical trial design was chosen to assess whether Z-Endoxifen HCl shows promise in providing greater in antitumor activity (in terms of increasing progression-free survival) than tamoxifen in postmenopausal women with metastatic ER positive breast cancer that is endocrine resistant.

This study will use a dynamic allocation procedure to allocate an equal number of patients to each of the treatment arm. This procedure will balance the marginal distributions of the stratification factors between these treatment arms. The stratification factors that will be used are: prior palbociclib and/or everolimus, type of disease and degree of endocrine resistance (see Section [4.8](#)).

All patients meeting the eligibility criteria who have signed a consent form and have begun treatment will be evaluable for assessment of all of the clinical endpoints. Patients will be included in the treatment group they were randomized to regardless of their actual treatment or duration of treatment. Summary statistics for patient and tumor characteristics, eligibility rates, length of follow-up, and treatment acceptance rates will be calculated by assigned treatment arm.

13.1.2 Definition and documentation of primary endpoint.

The primary endpoint is progression-free survival (PFS) defined as the time from randomization to documentation of local, regional or distant disease progression or death without progression of disease.

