13.3.2 Analysis methods

For each patient, the genetic alterations seen in their tumor biopsy and their circulating tumor cells will be compared to ascertain which genetic alteration was seen in both tumor biopsy materials and CTCs, seen in only their tumor biopsy material, or seen in only their CTCs. For each alteration observed, we will tabulate the proportion of patients who had the genetic alteration seen in both tumor biopsy materials and CTCs, the proportion of patients who had the genetic alteration seen in only their tumor biopsy material, the proportion of patients who had the genetic alteration seen in only their CTCs, and the proportion of patients who did not have the genetic alteration in tumor biopsy materials or CTCs.

Toy et al. conducted a genetic analysis of tumors taken from individuals with metastatic ER-positive breast cancer whose tumors had grown or spread to new sites after at least 3 months with hormonal therapy. They found in 14 (17.5%) of 80 cases there were mutations in *ESR1* affecting the ligand-binding domain. The prevalence of mutations in this gene among the tumors from the patients who relapsed on hormonal treatment was higher than that seen in The Cancer Genome Atlas (TCGA) invasive primary (untreated) breast cancer and luminal A and luminal B primary breast cancer cases, suggesting that these mutations may have a role in the development of acquired resistance to hormonal treatment.

For each treatment arm:

- a point and interval estimate of the proportion of patients with *ESR1* mutated CTCs prior to the start of treatment or is found to have *ESR1* mutated CTCs during treatment at or prior to progression will be determined using the properties of the binomial distribution
- a point and interval estimate of the proportion of patients with *ESR1* mutated CTCs prior to the start of treatment who progress within the first 4 months of treatment will be determined using the properties of the binomial distribution
- a point and interval estimate of the hazard of disease progression among the patients with *ESR1* mutated CTCs prior to the start of treatment or at end of the second cycle of treatment relative to patients who do not have *ESR1* mutated CTCs either prior to the start of treatment or at end of the second cycle of treatment will be constructed using the results of fitting a Cox model to time to progression data.

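### Two exploratory marker analyses need a small repair: ST1 plans no estimate of the between-arm contrast its objectives ask for, and one ST2 Cox model groups patients by a week-6 result without a landmark

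*Combined protocol and SAP*

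**What the plan says.** **ST1 (pre-treatment biopsy markers).** Objectives 2.3.1, 13.2.1 and 14.1.2 ask whether markers are associated with longer PFS or higher response in the Z-Endoxifen arm compared with the tamoxifen arm. Section 13.2.2 fits Cox and logistic models with the arms combined and within each arm. It states that this serves both prognostic and predictive aims in an exploratory way, and it names the ER and PI3K pathways as of primary interest. Section 13.2.4 plans within-arm response-rate differences for SRC3 and PKC beta 1, plus a proportional hazards model with no treatment-by-marker term.

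**ST2 (circulating tumor cells, CTCs).** The third bullet of Section 13.3.2 estimates, per arm, the hazard of progression by ESR1 status, taking those with "mutated CTCs prior to the start of treatment or at end of the second cycle of treatment relative to patients who do not have" them at either time. The estimate "will be constructed using the results of fitting a Cox model to time to progression data". No landmark, time-dependent covariate or time origin is given. The only origin the protocol defines for progression is in Section 13.1.2, where PFS is "defined as the time from randomization to documentation of local, regional or distant disease progression" or death. Section 6.2.4 lists the end-of-cycle-2 draw and "4) At the time of disease progression" as separate samples. The first bullet of Section 13.3.2 counts patients with ESR1 "mutated CTCs during treatment at or prior to progression"; the third does not name the progression sample.

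**The concern.** **ST1.** Pooled hazard ratios address prognosis. Two within-arm hazard ratios side by side invite a predictive reading but carry no interval for their ratio. A marker that looks favorable in one arm and neutral in the other may reflect chance alone, and the planned output would not show this.

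**ST2.** A patient who is negative at baseline can join the mutated group only through a result obtained six weeks into follow-up. If time runs from randomization, a patient who fails before giving a counted week-6 sample can never convert. Calling such patients negative puts early failures into the comparison group and makes mutation look protective. Excluding them removes early failures from that group only and makes mutation look harmful. The plan does not choose between these.

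**Working it through.** **Plan figures first.** Schoenfeld events for a hazard ratio of 0.5, one-sided alpha 0.10 and 95% power: 4 × (1.2816 + 1.6449)² / (ln 0.5)² = 71.3, so 72, as in Section 13.1.3. ST1 patients per arm: 40 × 0.73 = 29 and 40 × 0.95 = 38, as in Section 13.2.3. ESR1 mutation prevalence: 14/80 = 17.5%, as in Section 13.3.2. None of these is disputed.

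**ST1: precision of the missing contrast.** With d events per arm and marker prevalence q, the standard error of the log ratio of hazard ratios is √(2 / (d·q·(1 − q))). I take d = 0.9n, because 72 of 80 patients are to have events. The 95% interval factor is exp(1.96·SE). Power for a true ratio of 2 (two-sided 0.05) is Φ(ln 2 / SE − 1.96).

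| Marker, q | n per arm | SE | Interval: times or divided by | Power |
|---|---|---|---|---|
| ESR1, 0.175 (13.3.2) | 29 / 38 | 0.729 / 0.636 | 4.2 / 3.5 | 16% / 19% |
| SRC3, 0.25 (13.2.4) | 29 / 38 | 0.639 / 0.558 | 3.5 / 3.0 | 19% / 24% |
| PI3K pathway, 0.56 (13.2.3) | 29 / 38 | 0.558 / 0.487 | 3.0 / 2.6 | 24% / 30% |

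The 17.5% counts mutations only; amplification would raise q. Section 13.2.4 says PKC beta 1 prevalence is unknown, so it has no row.

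**ST2: how many patients are at issue.** Two 21-day cycles are 42 days, or 1.38 months. With exponential PFS at the design medians of 3 and 6 months, progression by week 6 is 1 − 2^(−1.38/3) = 27.3% on tamoxifen (10.9 of 40) and 1 − 2^(−1.38/6) = 14.7% on Z-Endoxifen (5.9 of 40).

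**ST2: direction and size under a null marker.** Settings of the simulation:
- 300,000 patients per setting; Cox model with Efron ties.
- Progression dated at the next scan, on the Section 11.1 schedule and on the calendar footnote E schedule.
- Censoring uniform over 9 to 24 months.
- Baseline prevalence 17.5%. This is the tumor figure, assumed to apply to CTCs.
- Assumed conversion of 5% to 30% of baseline-negative patients by week 6.
- Time runs as if treatment started at randomization; Section 7.0 allows up to 14 days.

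The documents do not give the share of week-6 progressors without a counted cycle-2 result, so it is varied. Hazard ratios, accurate to about 0.01:

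| Share without a counted result | Tamoxifen, called negative | Tamoxifen, excluded | Z-Endoxifen, called negative | Z-Endoxifen, excluded |
|---|---|---|---|---|
| 0% | 0.99–1.00 | 0.99–1.00 | 0.99–1.01 | 0.99–1.01 |
| 10% | 0.97–0.99 | 1.01–1.02 | 0.98–1.00 | 1.00–1.02 |
| 25% | 0.94–0.98 | 1.02–1.05 | 0.96–0.99 | 1.02–1.04 |
| 50% | 0.88–0.97 | 1.06–1.12 | 0.92–0.98 | 1.04–1.08 |
| 100% | 0.77–0.94 | 1.16–1.31 | 0.84–0.96 | 1.10–1.18 |

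A separate run with Breslow ties on the Section 11.1 schedule gave 0.81–0.95 and 1.16–1.30 for tamoxifen in the last row. The extreme therefore depends somewhat on method; the direction does not.

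**Size against noise.** The lowest tamoxifen value is ln 0.771 = −0.260. The mutated share there is 0.175 + 0.825 × 0.30 × 0.727 = 0.355, so SE = 1/√(36 × 0.355 × 0.645) = 0.348 and the shift is 0.75 SE. At a 10% share, ln 0.971 = −0.029, or 0.08 SE.

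**Landmark at week 6.** The null hazard ratio is 0.99–1.01. Patients kept are 40 × 0.727 = 29 and 40 × 0.853 = 34. Events kept are 27.1 of 38.0 and 26.2 of 32.1, so the standard error grows by √(38.0/27.1) = 1.18 and √(32.1/26.2) = 1.11.

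**The case against.** **On ST2.** A reader might infer that the ST2 hazard ratio carries a material immortal-time bias. The documents do not support that. The first scheduled scan falls at completion of cycle 2 (Section 11.1; calendar footnote E), at the same visit as the draw in Section 6.2.4, and the calendar says that "labs, scans, tests and observations may be obtained no more than +/- 3 days prior to day 1 of treatment". A sample taken at that visit is naturally read as the end-of-cycle-2 sample, and if it counts the bias is near zero. The extreme row needs every week-6 progressor to lack a counted result, and its 0.77 also needs 30% conversion in six weeks. Nothing in the documents indicates either. ST2 is optional (Section 4.7.1), so fewer patients would shrink the shift relative to its error: with half contributing, 0.75 × √0.5 = 0.53 SE. The second bullet of Section 13.3.2 already uses baseline status alone, though for a proportion progressing within four months and not for a hazard ratio.

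What stands is narrower. The plan never says that the shared-visit sample counts. Some patients can also leave before that visit: through death, through removal for radiation recorded as progression (Section 8.1.9), or as progression under Section 11.4.6, which covers "Patients with global deterioration of health status requiring discontinuation of treatment without objective evidence of disease progression at that time".

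**On ST1.** A reader might infer that the plan overlooks prediction. It does not: Section 13.2.2 names it as an aim, and Section 13.2.3 calls the work hypothesis generating. A reader might also infer that Section 13.2.4 confines its hazard model to within-arm fits, but those sentences do not repeat the within-arm phrase. Under either reading there is no between-arm term. A ratio could be worked out from the within-arm results, and it would be imprecise. Both remarks are fair, but neither supplies the estimate and interval that the objectives call for. The SET index is outside this point, because Section 14.1.3 already plans a PFS comparison between treatments.

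**Conclusion.** Both parts hold as repairs to exploratory analyses.

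**ST1** is a mismatch between objective and analysis: a between-arm question with no between-arm estimate or interval. The added estimate would be weak, with an interval of times or divided by about 2.6 to 4.2 and power of about 16% to 30% for a ratio of 2. It would show how little the within-arm contrasts can support. These figures assume 90% of patients have events, equally across arms and marker groups.

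**ST2** is a grouping rule that uses post-baseline information without a landmark. The bias is probably near zero, at most about three quarters of a standard error in the extreme case, and its direction depends on a handling choice left open. This rests on exponential PFS at the design medians and on the assumed conversion and missing-sample shares above.

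**What to change.** **ST1.** For the markers of primary interest only (ER/ESR1 pathway, PI3K pathway, SRC3, PKC beta 1), add two estimates:
- For PFS, the treatment-by-marker ratio of hazard ratios with its 95% interval.
- For response, the between-arm difference of the within-arm response-rate differences, with an interval that stays valid with zero responders. Section 1.3.4 cites a 0% response rate on tamoxifen after AI relapse, so an arm without responders is plausible.

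Label these exploratory and imprecise, and do not extend them to every gene and alteration type. This adds at most four estimates for each endpoint.

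**ST2.** Replace the third bullet of Section 13.3.2 with:
1. a hazard ratio by baseline CTC status, timed from randomization; and
2. a landmark analysis of status through end of cycle 2, in patients progression-free at that draw and timed from the draw.

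A rule on counting samples from a week-6 progression visit is needed only if the protocol's existing third-bullet model is kept.

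**Cost.** SAP wording only; no samples, visits or patients are added. At the design medians the landmark set loses about 11 tamoxifen and 6 Z-Endoxifen patients of 40, before non-consent and assay loss, and its standard error is about 18% and 11% wider. The baseline analysis keeps those patients.

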13.3.1 Objectives

- 13.3.1.1 To assess whether the molecular characteristics identified in the tumor biopsies are detectable in CTCs and/or cfDNA.
- 13.3.1.2 For each treatment arm, to examine ESR1 mutations or amplifications identified in CTCs or cfDNA change over time and explore the impact of these changes on PFS and response rates.

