14.2.1 Background

Comprehensive noninvasive monitoring of genetic alterations over time should help guide use of molecularly targeted drug therapies, including endocrine therapy for breast cancer. If the driving genetic alterations of an individual patient's tumor are known, monitoring those alterations globally through serial blood sampling as opposed to repeated tumor biopsies of a single site would allow clinicians to respond directly to changes in genetic alterations and allow for truly tailored drug selection. This "liquid biopsy" approach is clearly favorable from the perspective of patient comfort, health economics, and maximizing therapeutic efficacy, although controversy remains as to whether circulating tumor cells or circulating cell free DNA is more representative of underlying tumor biology. We propose to evaluate the peripheral blood for specific *ESR1* alterations identified in tumor biopsies and determine whether or not serial changes in those alterations correlate with patient outcomes relative to treatment with either tamoxifen or endoxifen.

Circulating Tumor Cells (CTCs)

That CTCs have biologic relevance in breast cancer is clear, as their relative abundance in the peripheral blood has strong correlations with disease related outcomes in both early stage and advanced disease [51-54]. The development of CTCs as a "liquid biopsy" by which to perform ongoing tumor assessments in relation to treatment exposure is possible with recent technologic advances that allow for the capture of CTCs with epithelial, EMT-like, and/or stem cell like phenotypes, and for molecular characterization by immunocytochemistry, fluorescence in situ hybridization, RT-PCR, and next generation sequencing. Mayo Clinic Rochester has access to several platforms for CTC capture and analysis with the goal of studying the most clinically relevant population of CTCs for a given translational research question.

Circulating Cell Free DNA (cfDNA)

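### The ST2 blood analysis plans no cfDNA estimate, has no rule for patients without captured CTCs, and sets a 4-month cut just before the week-18 scan

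*Combined protocol and SAP*

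**What the plan says.** **Objectives and samples.** Objectives 2.3.6 and 2.3.7, and their restatements in 13.3.1 and 14.2.2, cover both blood sources. Section 13.3.1.2 aims "to examine ESR1 mutations or amplifications identified in CTCs or cfDNA change over time and explore the impact of these changes on PFS" and response. Sections 6.2.4 and 14.2.3 collect CTC and cfDNA tubes at the same four visits: baseline, end of cycle 2, end of cycle 8 and progression. Section 14.2.3 applies the same mutation assay to CTC DNA and cfDNA. Section 14.2.1 says it is unsettled which source better represents the tumor.

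**Analysis.** Section 13.3.2 does not mention cfDNA. It says "the genetic alterations seen in their tumor biopsy and their circulating tumor cells will be compared". It then tabulates four groups: both, biopsy only, CTC only, and a remainder, "the proportion of patients who did not have the genetic alteration in tumor biopsy materials or CTCs". Three per-arm estimates follow, all based on ESR1-mutated CTCs:

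- the proportion of patients with mutated CTCs before or during treatment;
- among patients with mutated CTCs at baseline, the proportion "who progress within the first 4 months of treatment will be determined using the properties of the binomial distribution";
- a Cox hazard ratio for mutated CTCs at baseline or end of cycle 2, "relative to patients who do not have *ESR1* mutated CTCs either prior to the start of treatment or at end of the second cycle of" therapy.

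No set of CTC-evaluable patients is defined. On CTCs in general, Section 14.2.1 says "their relative abundance in the peripheral blood has strong correlations with disease related outcomes in both early stage and advanced disease".

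**Scans.** The study calendar (Section 5.1, note E) requires tumor measurements "at completion of cycles 2, 4, and 6 (approximately, every 6 weeks"). Cycles last 21 days, with a scan window of 3 days either side. Section 11.1 differs from the calendar after cycle 6, but both put scans at weeks 6, 12 and 18.

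**The concern.** Three gaps sit in one section.

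1. **cfDNA has objectives, samples and an assay, but no planned estimate.** Any cfDNA result would be defined after the data are in hand.
2. **The reference group has no entry condition.** A patient can be classed as mutated only if CTCs were captured and assayed. She can be classed as not mutated with no CTCs at all. If CTC burden is prognostic, the two groups differ in burden as well as in ESR1 status. The detection table likewise merges assayed and not found with nothing to assay.
3. **The 4-month limit is not aligned with the scans.** It ends just before a scheduled assessment, so the count depends heavily on what was documented one scan earlier.

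At stake are the readability of the exploratory ESR1 hazard ratio, the tissue-blood comparison and the early-progression proportion.

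**Working it through.** **Figures in the plan.** Section 13.3.2 gives one figure, an ESR1 mutation prevalence of 14/80 = 0.175, which reproduces. Section 13.1.3 gives 72 events. By the Schoenfeld formula, 4(1.2816 + 1.6449)² / (ln 0.5)² = 4 × 8.564 / 0.4805 = 71.3, rounded up to 72, which also reproduces.

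**cfDNA.** No arithmetic applies. The objectives and collection schedule name both sources. The biopsy comparison, the four-way table and the three per-arm estimates name CTCs only.

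**Reference group.** The documents give neither the fraction of patients with no captured CTCs nor the hazard ratio (HR) for captured versus none, so both are assumed over a range. A Cox model was fitted to 400,000 simulated patients with:

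- exponential PFS, median 3.0 months in patients with no captured CTCs;
- ESR1 prevalence 17.5%, independent of CTC status;
- patients with no captured CTCs placed in the reference group.

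| No CTCs captured (assumed) | CTC HR (assumed) | Fitted ESR1 HR, true 1.0 | Fitted ESR1 HR, true 2.0 |
|---|---|---|---|
| 20% | 1.5 to 2.5 | 1.11 to 1.29 | 2.13 to 2.37 |
| 40% | 1.5 to 2.5 | 1.21 to 1.54 | 2.25 to 2.79 |
| 60% | 1.5 to 2.5 | 1.31 to 1.83 | 2.41 to 3.21 |

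If CTC capture were not prognostic (CTC HR 1.0), mutated patients without captured CTCs would dilute a true HR of 2.0 to 1.84 to 1.94. Restricting to patients with captured CTCs returns 1.00 or 2.00, to within 0.01, throughout.

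**Precision.** Take 40 patients per arm, all joining ST2, and 72/2 = 36 events per arm. At most 0.175 × 40 = 7 mutated patients are expected. With 60% having no captured CTCs, 7 × 0.4 = 2.8 are expected. The 95% interval multiplies and divides the HR by exp(1.96 / √(36 p(1 − p))):

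- p = 0.175: exp(1.96 × 0.439) = 2.4
- p = 0.070: exp(1.96 × 0.653) = 3.6

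**The 4-month cut.** Four months is 4 × 30.4375 = 121.75 days. The end of cycle 6 is 6 × 21 = day 126, window 123 to 129. The cut falls 4.25 days before the nominal scan and 1.25 days before the window opens. The last scheduled scan inside it is week 12, day 84 (2.76 months). With exponential PFS at the design medians of Section 13.1.3, the proportion progressed by time t is 1 − 2^(−t/median):

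| Median | By 4 months | By the week-12 scan | By the week-18 scan (4.14 months) |
|---|---|---|---|
| 3.0 months | 60.3% | 47.1% | 61.6% |
| 6.0 months | 37.0% | 27.3% | 38.0% |

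On the nominal schedule the cut misses 60.3 − 47.1 = 13.2 points and 37.0 − 27.3 = 9.7 points.

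**The case against.** The strongest reply is that the plan contains no rule coding patients without CTCs as unmutated, that the size of any bias rests on invented inputs, and that all of this is exploratory.

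- **Coding.** A reader might infer that the plan assigns these patients to the unmutated group. It does not say so. The comparator could also mean CTCs captured and wild-type. What stands is the missing rule and its literal default.
- **Size.** Section 14.2.1 speaks of abundance, gives no figure and does not contrast presence with absence. Dilution works against the confounding. Grouping by end-of-cycle-2 status while timing from treatment start, which the calculation does not model, favors patients who reach that draw. This stands: the range shows what could happen and is not a prediction.
- **Consequence.** A reader might infer that ST2 would report ESR1 mutation as harmful on both drugs, and so mislead the trial's ESR1 hypothesis. With about 7 mutated patients per arm at most, it could not establish that. In the 40%, CTC HR 2.0 scenario the fitted HR of 1.39 has an interval factor of 2.9, or 0.48 to 4.03. Whether ESR1 alterations favor Z-endoxifen is addressed on tissue in ST1 (Sections 2.3.1 and 14.1.2.1). If CTC burden is equally prognostic in both arms, the bias would also largely cancel between them.
- **Detection.** Objective 13.3.1.1 asks whether biopsy findings are detectable in blood. A patient with no CTCs is a genuine non-detection, so dropping her would overstate detectability. This stands and shapes the fix.
- **Timing.** Deaths, symptomatic deterioration and unscheduled imaging can be recorded between scans, and the 3-day tolerance on each cycle (Sections 7.1 and 7.2) can move the week-18 scan either way. A reader might conclude that the result is simply a 12-week proportion; that is too strong. The percentages also apply whole-arm medians to a small subgroup: 13.2% of 7 patients is 0.9 of a patient.

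**Conclusion.** The point holds, at low severity. The cfDNA gap follows from the text and needs no assumption. The missing evaluability rule is also textual, and the confounding it could cause is plausible on the protocol's own statement about CTC abundance. Its amount is not determined: 1.1 to 1.8 under a true HR of 1.0 depends on an assumed 20% to 60% of patients without captured CTCs and an assumed CTC HR of 1.5 to 2.5. The 4-month cut is misaligned on the nominal schedule by about 10 to 13 percentage points at the design medians, softened by events recorded between scans and by schedule drift. ST2 is optional and has no test or power statement, and the primary PFS comparison is untouched.

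**What to change.** In Section 13.3.2:

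1. Produce the biopsy comparison, the proportions and the Cox estimate for cfDNA and for an either-source ESR1 definition, as well as for CTCs.
2. Base the CTC Cox contrast on patients with evaluable CTC DNA, with no CTCs captured as a separate group. In the detection table keep every patient, give no CTCs captured its own category, and report proportions with both denominators. This does not remove confounding by CTC abundance among patients who have CTCs; the simulated recovery is exact only because CTC status was treated as yes or no.
3. Replace the 4-month limit with progression documented at or before the end-of-cycle-6 (week 18) assessment, including its window.

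The cost is wording and a few more exploratory tables, with no new samples. The CTC-only Cox contrast will have fewer patients. The changes should be made before the ST2 data are analyzed.
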